## **B** Background

#### B1 Prior Literature and Studies and Rationale for this Study

Thumb carpometacarpal osteoarthritis (CMC OA) is a common disease, affecting up to 25% of women and 8% of men, and is increasing in prevalence with the aging population. When symptomatic, loss of thumb function can impart up to 50% impairment to the upper extremity. Nonoperative treatments for thumb CMC OA include activity modification, splinting, anti-inflammatory medications, and intra-articular corticosteroid injections. When nonoperative treatments fail, surgery may be considered.

Surgeries for advanced thumb CMC OA all incorporate trapezium excision to eliminate painful bony contact. The majority of hand surgeons in the United States supplement trapeziectomy with suspension using the FCR tendon (Figure **1)**. This suspensionplasty is touted to reduce subsidence of the thumb metacarpal and improve pinch strength over simple trapeziectomy. However, LRTI using the FCR tendon increases surgical time, increases perioperative complications, and increases costs of surgery. Postoperatively, patients are typically placed in rigid immobilization for 4-6 weeks and require 3 months of healing prior to strengthening. Despite both the popularity and heightened direct/indirect costs, comparative studies have not demonstrated any long term benefit of LRTI over simple trapeziectomy and hematoma arthroplasty. Gangopadhyay et al randomized 174 thumbs to trapeziectomy alone, LRTI, or trapeziectomy and palmaris longus interposition. Of the 153 thumbs with ≥5 years follow-up, 78% had good results and pain relief was durable, and there were no differences in pain, function (grip/pinch strength), or complications among the three groups. In their 2015 Cochrane Review, Wajon et al demonstrated no benefit to pain or function from LRTI compared to simple trapeziectomy, although they acknowledged that the evidence was of low quality.

**Figure 1**: Steps in trapeziectomy with LRTI. **A**: Trapeziectomy. **B**: Reconstruction performed with a LRTI using FCR tendon. Radial half of FCR tendon passed through a tunnel in base of first metacarpal. **C**: Tendon sutured to itself as a space-filling arthroplasty, augmented by Kirschner wire to prevent subsidence.

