Hand surgeons, however, continue to perform LRTI secondary to the desire to provide mechanical support for the thumb metacarpal and to avoid the exposed Kirschner wires (K-wires) associated with simple trapeziectomy. Recently, techniques have been described that provide immediate internal suspension of the thumb metacarpal after trapeziectomy without requiring prolonged immobilization or painful K-wires. Internal brace (IB, **Figure 2)**, a technology used in ligament augmentation in lateral ankle instability, syndesmosis injuries, and scapholunate ligament reconstruction , has been used at our institution for thumb CMC OA with encouraging outcomes in the short-term (unpublished data). The IB procedure allows the patient to forego postoperative casting or K-wire pinning and return to all activities at 6 weeks.

**Figure 2**: Illustration of internal brace procedure. Trapeziectomy is performed in standard fashion. Longitudinal traction is applied to the thumb. A suture anchor with suture tape is inserted into a drill hole at the radial aspect of the thumb metacarpal base. A second suture anchor is inserted into a drill hole at the radial base of the index metacarpal such that the suture tape suspends the thumb at the natural groove. Thumb position and tension are then assessed.

To date, the literature lacks high level clinical evidence to define IB's role in the treatment of thumb CMC OA. A prospective, randomized controlled trial (RCT) is required to compare the procedure's effectiveness in relieving pain and restoring function against that of LRTI. Therefore, we propose a pilot RCT comparing patient-reported outcomes following IB and LRTI to establish feasibility and generate effect size and variability estimates for a definitive, subsequent RCT (Aims 1 & 2). Recognizing that objective clinical measures such as thumb range of motion, grip/pinch strength, radiographic outcomes, and complications/need for additional surgery are critical in measuring IB's effectiveness against LRTI, we will characterize the two procedures with respect to these parameters along with return to work/activity (Aim 3).

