## C Study Objectives

#### C1 Study Aims and Rationale for Selection of Outcome Measures

Aim 1: Establish feasibility of a definitive trial by determining the proportion of eligible subjects who agree to randomized treatment and determining the followup retention rate. Rationale: To date, no studies have compared IB and LRTI for thumb CMC OA. Our study will assess the feasibility of a prospective RCT comparing outcomes of the two procedures. Hypothesis: A prospective RCT comparing outcomes of IB and LRTI is feasible, as defined by the ability to successfully recruit and randomize  $\geq$ 50 patients over the course of 1 year with a follow-up retention rate of  $\geq$ 90%.

Aim 2: Estimate effect sizes and variability in patient-reported outcomes for planning a definitive, two-arm RCT. Rationale: We will assess patient-reported outcomes (PROMIS UE/physical function, VAS pain, VAS satisfaction) following IB and LRTI. Effect size and variability estimates are required to inform the design of a future definitive trial. Hypothesis: IB will produce superior patient-reported outcomes to those of LRTI at 6 weeks and 3 months.

Aim 3: Characterize objective clinical outcomes (thumb range of motion, grip/pinch strength, radiographic outcomes, and complications/need for additional surgery) and to identify differences in return to work/activity following IB and LRTI at three months. Rationale: Objective clinical outcomes are important predictors of patient function after surgery for thumb CMC OA. IB offers an expedited return to work and activity by allowing patients to forego postoperative casting. Hypothesis: IB will produce similar objective outcomes to LRTI with a quicker return to work/activity.

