Patients will undergo a standardized postoperative recovery and therapy regimen:

#### Study Aims 2 & 3

PROMIS Physical Function and Upper Extremity scores will be collected at all clinic visits on iPad as per standard protocol for all patients presenting to a Washington Orthopaedic Surgery clinic. Thumb Universitv ROM at carpometacarpal. metacarpophalangeal, and interphalangeal joints will be collected by a member of our team at 4 weeks, 3 months, and 1 year after surgery. Visual Analog Scale Pain and Satisfaction scores will be collected by a member of our team at 2 weeks, 4 weeks, 3 months, and 1 year post-op. Grip and pinch strength (3-point and lateral vs contralateral values and vs preoperative values) will be collected at pre-op visit and all post-op visits except the 2 week visit. Radiographic subsidence will be measured via C-arm radiographs at 3 months and 1 year post-op. Complications (mild, moderate, severe) will be recorded throughout the course of the study at all time points. Mild complications will be defined as those with minor clinical impact (i.e., scar tenderness or sensory disturbances). Moderate complications will be defined as clinically relevant with delay in patient recovery, but not severe enough to necessitate revision surgery and resolve by 12 months after surgery (i.e., mild CRPS type I, tendinitis, neuromas treated with steroid injections). Severe complications will be defined as those which result in revision surgery, pain at rest, or impaired hand function at 12 month exam (i.e., severe CRPS) type I or tendinitis and neuromas that do not improve with corticosteroid injections and require surgery). We will document patient return to work/activity at each follow-up appointment.

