## F2 Analysis Plan and Statistical Methods

Patient demographic and clinical characteristics will be summarized using means (standard deviation, SD) or median (25th, 75th) for continuous variables and frequency (percentage) for categorical variables. The recruitment rate (95% confidence interval) will be reported as the number randomized out of the total number of participants approached to participate in the study (screened). Reasons for not wanting to participate will be summarized and reported. The effect sizes and variability of the PROMs for each group will be reported and used to determine the sample size for a larger definitive trial. Differences in PROMs between LRTI and IB at 6 weeks and 3 months will be examined using a two-sample t-test and differences in categorical outcomes (return to work/activity, yes/no, at 3 months) using Pearson chi-squared test. Changes over time will be evaluated graphically to see the trajectory of change over follow-up and for assessing critical time points to inform future study design parameters. Objective parameters will be summarized for each group using descriptive statistics. The significance level will be 0.05 for all tests due to the exploratory nature of the study.

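### Patient-reported outcomes are compared between arms only at 6 weeks and 3 months, at the edge of the usual LRTI restrictions; the 1-year scores are collected, but no numerical between-arm estimate is specified for them

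*Combined protocol and SAP*

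**What the plan says.** The hypothesis for Aim 2 (C1) is that "IB will produce superior patient-reported outcomes to those of LRTI at 6 weeks and 3 months". F2 tests it at those two times and no others: "Differences in PROMs between LRTI and IB at 6 weeks and 3 months will be examined using a two-sample t-test".

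Two further sentences in F2 bear on later follow-up. One is graphical: "Changes over time will be evaluated graphically to see the trajectory of change over follow-up". The other concerns planning and names no time point: "The effect sizes and variability of the PROMs for each group will be reported"; these results are then to be used to size the definitive trial.

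Clinic visits are set at weeks 2 and 4, month 3 and year 1 (D1, E2). "PROMIS Physical Function and Upper Extremity scores will be collected at all clinic visits", so PROMIS is available at 1 year, and VAS pain and satisfaction are also scheduled then.

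On aftercare, B1 says of LRTI that "patients are typically placed in rigid immobilization for 4-6 weeks and require 3 months of healing prior to strengthening". Of the alternative it says: "The IB procedure allows the patient to forego postoperative casting or K-wire pinning and return to all activities at 6 weeks". Aim 3 in C1 credits the faster return to work and activity to the absence of a cast.

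**The concern.** Both comparison times lie where aftercare is likely to differ between the arms. A score difference at either time combines what the operation did with what each group had been allowed to do up to then. B1 says a randomized trial is needed to "compare the procedure's effectiveness in relieving pain and restoring function against that of LRTI", and early scores alone say little about whether an advantage lasts once both groups are unrestricted.

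What is at stake is Aim 2, which exists to supply effect sizes and variability for the next trial. If its planners have a numerical contrast only at the early times, they have no estimate, interval or SD for the period after restrictions end. A plot does not supply these. B1 also reports no long-term benefit of LRTI over simple trapeziectomy. That evidence does not involve IB, but it makes fading of an early difference plausible enough to be worth measuring.

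**Working it through.** **The plan's own figure.** The plan gives no effect size, SD or power for the patient-reported outcomes. Its only computed figure (F1) is the 95% interval for a 50% randomization rate with n = 100. The Wilson score formula reproduces it: centre 0.5; half-width = 1.96 × √(0.25/100 + 1.96²/(4 × 100²)) / (1 + 1.96²/100) = 0.0962, giving 0.404 to 0.596. It has no bearing on this point.

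**Timing, from B1 (3 months taken as 13 weeks).**

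| Time | LRTI, typical | IB |
|---|---|---|
| 6 weeks | 0 to 2 weeks out of immobilization (6 − 6 to 6 − 4) | not cast; full activity just starting |
| 3 months | strengthening may just begin | about 7 weeks of full activity (13 − 6) |
| 1 year | past both restriction periods | past the restriction period |

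The contrast in restrictions is clearer at 3 months than at 6 weeks, when IB patients have themselves only just been released.

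**What a 1-year estimate would deliver.** Inputs: 50 patients (F1); a retention target of at least 90% (C1, no time point given). Assumptions: 1:1 allocation, which the plan does not state; two-sided 0.05; no covariate adjustment. With m patients per arm, the 95% half-width in SD units is t(0.975, 2m − 2) × √(2/m). At 90% retention m = 22.5, so 2.017 × √(2/22.5) = 2.017 × 0.298 = 0.60. The last two columns use the two-sample t-test (noncentral t).

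| Retention | m per arm | Half-width (SD) | Detectable at 80% power (SD) | Power if true difference is 0.5 SD |
|---|---|---|---|---|
| 100% | 25 | 0.57 | 0.81 | 0.41 |
| 90% | 22.5 | 0.60 | 0.85 | 0.38 |
| 80% | 20 | 0.64 | 0.91 | 0.34 |
| 70% | 17.5 | 0.69 | 0.98 | 0.30 |

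**Why the planning time point matters.** The effects here are assumed, since the documents give none. At 80% power and two-sided 0.05, a definitive trial needs 64 per arm for 0.5 SD, 176 for 0.3 SD and 394 for 0.2 SD. The pilot could not tell these apart at 1 year: the gap from 0.5 to 0.2 is 0.3 SD, half of the 0.60 SD half-width.

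**Calendar.** Aim 1 allows 1 year of recruitment, so the last 1-year visit falls no earlier than month 12 + 12 = 24. H4 lists analysis and manuscript submission under 12 months. Even if enrolment ended at month 6, as H4 suggests, the last 1-year visit would fall no earlier than month 18.

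**The case against.** The strongest reply is that the early comparison is what the trial set out to make. A1 and A3 describe the expected benefit as short-term, the hypotheses name 6 weeks and 3 months, and C1 presents the absence of a cast as part of what IB offers. A comparison of whole packages at early times answers that question. Feasibility is the primary outcome, and F2 calls the testing exploratory. All of this stands, and it makes the point one of completeness and interpretation rather than an invalid analysis.

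Four stronger readings are tempting, and the documents do not support them.

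- A reader might infer that the 1-year scores go unused. They do not: F2 plans trajectories partly to identify critical time points for future design, and its effect-size sentence is not limited to early visits. What is missing is a specified numerical estimate.
- A reader might infer that a 1-year comparison would separate the operation from the cast. It would not, because each arm remains surgery plus aftercare. Separating them would require a design in which aftercare did not differ by arm.
- A reader might infer that the definitive trial will be sized on the early contrast. No section says so; the risk is conditional.
- A reader might treat the B1 restriction times as this trial's rules. The LRTI times are background, qualified as typical. D1 introduces a standardized regimen whose content is not visible in the text available for review, so arm-specific aftercare is inferred, with support from Aim 3.

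Nor do the documents show how far restrictions lower PROMIS scores, and the argument is weaker for VAS pain and satisfaction.

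**Conclusion.** The point holds in a limited form. F2 specifies between-arm comparisons of patient-reported outcomes only at two times that, on the background account, sit at the edge of LRTI restrictions. It specifies no numerical contrast at the one scheduled visit clearly beyond them, although the data will be there. An early difference should be read as the effect of each procedure with its aftercare.

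The gain from adding the 1-year estimate is real but modest: a half-width of 0.57 to 0.69 SD for retention from 100% to 70%, assuming 1:1 allocation. It can show whether a large difference persists. It cannot confirm a moderate one or by itself protect the next trial from being mis-sized. The primary feasibility outcome is unaffected.

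**What to change.** - **F2:** pre-specify, for each patient-reported outcome, the 1-year between-arm difference with 95% confidence interval and pooled SD, labelled exploratory. Report it beside the early estimates and say that both will be considered in planning the definitive trial.
- **A2, the expected results closing B1, and Aim 2 in C1:** describe early differences as effects of each procedure with its aftercare. Use the 1-year estimate only to say whether a difference persists.
- **H4:** reconcile the timetable with Aim 1's recruitment year and the 1-year visit.
- **F2 against D1 and E2:** reconcile the 6-week comparison with a visit schedule that contains no 6-week visit.

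No new visit or measurement is needed for the 1-year estimate. The costs are a narrower early claim, an imprecise added estimate, and a final analysis that waits for 1-year data.

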#### 2.c Subject Recruitment Plans and Consent Process

The team will review patients' medical records and radiographs to determine potential participants' eligibility. The team will recruit eligible individuals during their clinic appointments using an information form outlining the benefits and relative limitations of each procedure. Patients who are interested in participating in the study will undergo initial testing at their clinic appointment, at which time they can also provide informed consent.

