#### E2 Schedule of Measurements, Visits, Safety and Adverse Events

Patients will undergo the surgery to which they are randomized, either LRTI or IB, performed by one of the seven Washington University orthopaedic hand surgeons. All patients will follow-up in clinic 2 weeks, 4 weeks, 3 months, and 1 year post-operatively.

PROMIS Physical Function and Upper Extremity scores will be collected at all clinic visits on iPad as per standard protocol for all patients presenting to a Washington University Orthopaedic Surgery clinic. Thumb ROM at carpometacarpal, metacarpophalangeal, and interphalangeal joints will be collected by a member of our team at 4 weeks, 3 months, and 1 year after surgery. Visual Analog Scale Pain and Satisfaction scores will be collected by a member of our team at 2 weeks, 4 weeks, 3 months, and 1 year after surgery. Visual Analog Scale Pain and Satisfaction scores will be collected by a member of our team at 2 weeks, 4 weeks, 3 months, and 1 year post-op. Grip and pinch strength (3-point and lateral vs contralateral values and vs preoperative values) will be collected at pre-op visit and all post-op visits except the 2 week visit. Radiographic subsidence will be measured via C-arm radiographs at 3 months and 1 year post-op. Complications (mild, moderate, severe) will be recorded throughout the course of the study at all time points. Mild complications will be defined as those with minor clinical impact (i.e., scar tenderness or sensory disturbances). Moderate complications will be defined as clinically relevant with delay in patient recovery, but not severe enough to necessitate revision surgery and resolve by

12 months after surgery (i.e., mild CRPS type I, tendinitis, neuromas treated with steroid injections). Severe complications will be defined as those which result in revision surgery, pain at rest, or impaired hand function at 12 month exam (i.e., severe CRPS type I or tendinitis and neuromas that do not improve with corticosteroid injections and require surgery). We will document patient return to work/activity at each follow-up appointment.

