# F Statistical Plan

## *F1* Sample Size Determination and Power

Various methods are identified in the literature for formulating a pilot study sample size. Julious recommends a minimum sample size of 12 per group as a rule of thumb and justifies this based on rationale about feasibility and precision about the mean and variance. So as to align our study with these recommendations, we plan to enroll 50 patients total in our pilot/feasibility study.

Approximately 100 patients per year undergo surgical intervention (either IB or LRTI) for CMC OA at Washington University. Assuming a 50% randomization rate for this study, a sample size of 100 produces a two-sided 95% confidence interval with a lower limit of 0.404 and upper limit of 0.596 when the sample proportion is 0.5. The primary goal of the trial is to assess feasibility and to obtain estimates for planning a larger, more definitive study to detect meaningful changes in clinical outcome measures.

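### F2 leaves the routinely collected preoperative PROMIS scores out of the arm comparison, which costs precision and leaves the inputs for a baseline-adjusted definitive trial unreported

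*Combined protocol and SAP*

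**What the plan says.** F2 sets out the comparison: "Differences in PROMs between LRTI and IB at 6 weeks and 3 months will be examined using a two-sample t-test". It mentions no covariate, change score or longitudinal model; the time course is described only in plots ("Changes over time will be evaluated graphically to see the trajectory of change over follow-up"). On planning the next trial it says: "The effect sizes and variability of the PROMs for each group will be reported and used to determine the sample size". On testing: "The significance level will be 0.05 for all tests due to the exploratory nature of the study".

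The PROMIS data are described in E2 (and likewise in D1): "PROMIS Physical Function and Upper Extremity scores will be collected at all clinic visits on iPad as per standard protocol". That routine covers every patient who presents to the orthopaedic clinic. Section 2.c places recruitment at such an appointment: "Patients who are interested in participating in the study will undergo initial testing at their clinic appointment". It does not say what the testing consists of. No section names a preoperative PROMIS score as a study baseline.

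VAS pain and satisfaction are scheduled only after surgery. Follow-up visits are at weeks 2 and 4, month 3 and year 1.

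**The concern.** A preoperative PROMIS score should be on file for each patient at no extra cost, and the named analysis does not use it. If that score predicts the follow-up score, an unadjusted comparison carries variance that could be removed, and any chance difference between the arms at baseline passes in part into the estimate.

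PROMs are secondary outcomes, but Aim 2 exists to supply effect and variability estimates for a definitive two-arm trial, and F1 counts such estimates within the primary goal. A definitive trial with a baseline-adjusted analysis is sized on the between-arm difference and the residual SD, or equivalently on the raw SD and the baseline to follow-up correlation. F2 asks for neither the residual SD nor the correlation.

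**Working it through.** **The plan's own figure.** The only computed figure is in F1: an interval of 0.404 to 0.596 for a randomization rate of 0.5 with n = 100. The Wilson formula, (p + z²/2n ± z√(p(1−p)/n + z²/4n²)) / (1 + z²/n), gives 0.4038 to 0.5962, which matches. It concerns feasibility and does not bear on this point. The plan states no SD, effect size or power for the PROMs.

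**Inputs.** From F1: "we plan to enroll 50 patients total in our pilot/feasibility study". The allocation ratio is not stated; I assume 1:1, so 25 per arm. F2 gives alpha 0.05 without sidedness; I assume two-sided. The documents give no correlation r between baseline and follow-up; I assume 0.3 to 0.6. Results are in units of the follow-up SD, taken as equal before and after surgery.

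**1. Unadjusted comparison.** SE = √(2/25) = 0.283 SD. The 95% CI half-width is t(48 df) × SE = 2.011 × 0.283 = 0.569 SD.

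**2. Baseline-adjusted comparison.** Residual variance is 1 − r² of the raw variance. The half-width is t(47 df) × 0.283 × √(1 − r²) × √(1 + 1/46); the last factor is an approximate small-sample cost of one covariate.

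| r | Variance ratio | Equivalent N, 50/(1 − r²) | Half-width, 25 per arm (t-test 0.569) | Half-width, 22.5 per arm (t-test 0.601) |
|---|---|---|---|---|
| 0 | 1.00 | 50 | 0.575 | 0.609 |
| 0.3 | 0.91 | 55 | 0.549 | 0.581 |
| 0.5 | 0.75 | 67 | 0.498 | 0.527 |
| 0.6 | 0.64 | 78 | 0.460 | 0.487 |

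The 22.5 per arm column reflects the 90% retention target in Aim 1 (45 of 50), with the formula's degrees of freedom and small-sample factor changed to match.

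**3. Chance imbalance.** The baseline difference also has SE 0.283 SD, so P(|difference| > 0.3 SD) = 2 × (1 − Φ(0.3/0.283)) = 0.29. The unadjusted estimate moves by r times the imbalance: at r = 0.5, an imbalance of 0.3 SD moves it by 0.15 SD, about half a standard error.

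**4. Sizing the definitive trial.** For an illustrative difference of 0.5 SD, 90% power and two-sided 0.05, total N = 4 × ((1.96 + 1.2816)/0.5)² = 168 with the raw SD. With the residual SD it is 168 × 0.91 = 153 (r = 0.3) or 168 × 0.64 = 108 (r = 0.6). Using the raw SD for an adjusted analysis therefore oversizes the trial by a factor 1/(1 − r²) of 1.10 to 1.56.

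**5. How well the pilot would estimate r.** With 50 patients and an observed r of 0.5, Fisher's transformation gives 0.549 ± 1.96/√47 = 0.549 ± 0.286, or 0.26 to 0.68 on the r scale. Applied to the 168 above, that spans 168 × (1 − 0.26²) = 157 down to 168 × (1 − 0.68²) = 90 patients.

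**The case against.** The strongest reply is that nothing here is invalid. Under randomization the t-test is unbiased and keeps its alpha, and chance imbalance is already in its standard error. PROMs are secondary in a feasibility pilot, the tests are labelled exploratory, and patient-level data sit in REDCap, so the correlation and residual SD could be computed later. D1 also says a retrospective cohort will inform sizing. The gain depends on an assumed r: at r = 0.3 the half-width shrinks only from 0.569 to 0.549 SD, and at r = 0 adjustment is slightly worse. All of this stands, and it limits the consequence.

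It can also be said that F2 does not state whether raw or change scores are compared. That does not rescue the plan. The variance of a change score is 2(1 − r) times the raw variance, which exceeds 1 − r² by (1 − r)², so ANCOVA is the more precise choice at any r below 1. F2 names one method, and a better one is available with the same data.

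A reader might infer more than the documents support:

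- That F2 produces the wrong SD. It does not. The raw follow-up SD is correct for a definitive trial analysed by t-test and conservative for an adjusted one, and the documents do not fix that trial's analysis.
- That every PROM and every visit is affected. The tests are at two time points only, and the VAS scores have no preoperative measurement.
- That patients who miss a visit are dropped. F2 gives no missing-data rule, and D1 provides for remote PROMIS completion when visits are missed.

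**Conclusion.** The point holds as one of efficiency and reporting, not validity. Assuming 25 per arm and r of 0.3 to 0.6, adjusting PROMIS for its preoperative score cuts the variance of the between-arm difference by about 9% to 36%, worth roughly 5 to 28 extra patients; if r is near zero almost nothing is lost. The raw SD is usable, but it would oversize a baseline-adjusted definitive trial by a factor of 1.10 to 1.56 under the same assumption, and the quantities needed to avoid this are not planned outputs. The correlation is my assumption throughout. That a preoperative PROMIS score exists is a sound inference from D1, E2 and 2.c, though the protocol does not state it as a study measurement. The feasibility endpoint is unaffected; Aim 2 would benefit.

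**What to change.** In F2, and in the measurement schedule in D1 and E2:

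- Define the last PROMIS score recorded before randomization as the study baseline.
- Replace the PROMIS t-tests with ANCOVA adjusting for that score. A repeated-measures model that includes baseline is an option, not a requirement.
- Report the adjusted between-arm difference with its 95% CI, plus the raw SD, the residual SD and the baseline to follow-up correlation with its CI.
- Size the definitive trial over a range of correlations, because 45 to 50 patients estimate r imprecisely.
- First reconcile the 6-week analysis time with the visit schedule, which has no visit at 6 weeks. No PROM analysis at that time is defined until this is settled.

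The change applies to PROMIS only; VAS pain and satisfaction have no preoperative score to adjust for. It costs one degree of freedom and a few sentences of protocol and SAP wording, and no new PROMIS data if the routine clinic collection happens as described.

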## A2 Primary Hypothesis

Our central hypothesis is that a prospective, randomized trial comparing LRTI and IB is feasible, and that IB will produce superior patient-reported outcomes to LRTI at 6 weeks and 3 months with an expedited return to work/activity.

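### Faster return to work or activity is hypothesised, but the plan tests only yes/no at 3 months and specifies neither a return date nor a time-to-return estimate

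*Combined protocol and SAP*

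**What the plan says.** The hypotheses are about speed. Section A2 expects better patient-reported outcomes after IB "with an expedited return to work/activity". The Aim 3 hypothesis in C1 is that "IB will produce similar objective outcomes to LRTI with a quicker return to work/activity". The Aim 3 objective in the same section fixes a time point: "to identify differences in return to work/activity following IB and LRTI at three months".

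Section B1 gives the expected timing. After IB, patients can "forego postoperative casting or K-wire pinning and return to all activities at 6 weeks". After LRTI they are immobilised for 4 to 6 weeks and "require 3 months of healing prior to strengthening".

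On data collection, E2 states: "We will document patient return to work/activity at each follow-up appointment". The appointments are given as: "All patients will follow-up in clinic 2 weeks, 4 weeks, 3 months, and 1 year post-operatively". The text does not say whether a status or a date is recorded.

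On analysis, F2 plans to test "differences in categorical outcomes (return to work/activity, yes/no, at 3 months) using Pearson chi-squared test". It also promises graphs of change over time, without naming the outcomes to be plotted.

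**The concern.** A yes/no status at one time is a coarse indicator of speed. If nearly everyone in both arms is back by 3 months, a real difference of some weeks barely shows. If the proportions do differ, the result still does not say by how much return was shortened, which is the benefit claimed for IB and something a definitive trial would want to know.

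The visit schedule does not repair this. The 6-week return expected after IB falls between the 4-week and 3-month visits. If only status is recorded, a return in that window is known only to lie somewhere in about 13 − 4 = 9 weeks.

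The outcome is also one combined item. Entry requires age 50 or older but not employment (D2, 2.a and 2.b), so it is unclear what return means for a patient who was not working before surgery. Dates that are not collected prospectively are hard to recover later.

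**Working it through.** **The plan's own figures.** The plan gives no power or precision for this outcome. Its only computed figure, the interval 0.404 to 0.596 in F1, concerns the randomization rate. It reproduces as a Wilson interval (0.4038 to 0.5962) and has no bearing here.

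**Inputs from the documents.** 50 patients (F1), significance level 0.05 (F2), visits as in E2, and 6 weeks for IB (B1).

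**Assumptions.** Equal arms of 25, complete data, two-sided tests, 3 months = 13 weeks, Weibull return times, 6 weeks taken as the IB median, and LRTI medians of 8 to 12 weeks. The documents give no LRTI return rate, so a range is needed.

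**Step 1: proportion returned by 13 weeks.** With median m and shape k, F(13) = 1 − exp[−ln 2 × (13/m)^k]. For k = 2:
- IB, m = 6: 1 − exp(−0.693 × 4.694) = 0.961.
- LRTI, m = 9: 1 − exp(−0.693 × 2.086) = 0.764.

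**Step 2: power.** For the planned test, sum the exact binomial probabilities over all outcomes where (p1 − p0)² / [p(1 − p) × 2/25] exceeds 3.841, with p the pooled proportion. For the log-rank test on dates, use 4,000 simulated trials per scenario, censored at 52 weeks. Entries are planned Pearson test / log-rank on dates.

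| LRTI median (weeks) | shape 1 | shape 2 | shape 3 |
|---|---|---|---|
| 8 | 13% / 17% | 30% / 51% | 4% / 83% |
| 9 | 21% / 28% | 58% / 79% | 37% / 98% |
| 10 | 30% / 42% | 79% / 93% | 82% / 99.8% |
| 12 | 48% / 65% | 97% / 99.6% | 99.8% / 100% |

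The 4% entry arises because 99.9% and 95% have returned by 13 weeks.

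**Step 3: a different distribution.** With lognormal times (coefficient of variation 0.5, IB median 6, 2,000 simulated trials), power for the planned test / log-rank on dates / log-rank on visit status is 23 / 50 / 38% at LRTI median 8, 44 / 79 / 65% at 9, 67 / 93 / 84% at 10, and 94 / 99.6 / 98% at 12. The direction is the same.

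**Step 4: what a 3-month result says about weeks gained.** Solve Step 1 for the median: m = 13 × [ln 2 / (−ln(1 − p))]^(1/k). Take 95% versus 70% returned, with the same shape in both arms:
- k = 1: 7.48 − 3.01 = 4.5 weeks.
- k = 2: 9.86 − 6.25 = 3.6 weeks.
- k = 3: 10.81 − 7.98 = 2.8 weeks.

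The 3-month proportions alone cannot tell these apart.

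**Step 5: what dates would give.** In the Weibull simulations, the 95% confidence interval for the difference in mean weeks (restricted to 52) has a half-width of 1.4 to 6.5 weeks. At LRTI median 9 and shape 2, the result is 3.2 ± 2.3 weeks.

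**The case against.** The strongest reply is that the F2 test does what the Aim 3 objective asks, a comparison at three months, and that a higher proportion returned by a fixed time is a legitimate measure of quicker return. That is true of the time point. It does not supply the number of weeks.

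Second, status at every visit already allows a grouped time-to-event analysis. Under Weibull times this is close to the planned test in most scenarios (58% for both at median 9, shape 2). It recovers more where the planned test is weakest (about 28% against 4% at median 8, shape 3) and under lognormal times. So visit status can help the test, but F2 does not plan such an analysis, and status cannot place a return within the interval between visits.

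Third, the 9-week gap rests on the E2 schedule, whereas A2, C1 and F2 refer to outcomes at 6 weeks. Those sections must be reconciled. If a 6-week visit replaced the 4-week one, the gap would shrink to 13 − 6 = 7 weeks; visit status would then give about 64% power against 78% with dates (median 9, shape 2). The gap argument is conditional; the absence of a time-to-return estimate is not.

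Fourth, the data collection forms are not in the documents, so a date field may exist. In that case only F2 needs changing.

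Finally, nearly all inputs to the power table are assumed, and B1's 6 weeks is when activity is allowed, not an observed median. The 3 months of healing before strengthening may also mean that many LRTI patients have not returned by 3 months, which is where the planned test does well. This is why the finding rests on the text and not on any one power figure.

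**Conclusion.** The concern holds. The hypothesis is about how soon patients return; the only named analysis is whether they have returned by 3 months; and nothing in the documents specifies a return date or a time-to-return estimate. The planned analysis therefore cannot say how many weeks IB saves. That conclusion does not depend on the simulations.

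The size of the power loss is uncertain: almost nothing if LRTI return is slow (median 12 weeks, shape 2 or 3), and up to 83 − 4 = 79 points if nearly all patients in both arms are back by 3 months. These figures assume 25 per arm with complete data and the return-time curves stated above.

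The outcome is secondary and exploratory and the feasibility endpoints are unaffected, so the weight is modest. Even so, F1 makes estimates for planning a larger trial part of the primary goal, and the change should be made before data collection.

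**What to change.** - At the visits already planned, record the calendar date of return to work for patients employed before surgery and, separately, the date of return to usual activity. Add a pre-operative employment item.
- In F2, add Kaplan-Meier curves by arm and the difference in median or restricted mean weeks to return with a 95% confidence interval, censoring at last contact. Use the log-rank test as the exploratory test.
- Keep the 3-month yes/no comparison with the Pearson test as a supporting analysis, and report the risk difference with a confidence interval.

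The cost is two REDCap date fields, one employment item and a few lines in F2, with no extra visits. The downsides are minor recall error in the dates and, for the work-only analysis, fewer patients and so a wider interval.
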